### **Introduction**

This study focuses on public support for prison nutrition standards—a policy that would require U.S. prisons to serve meals that abide by the USDA Dietary Guidelines for Americans. Specifically, we aim to examine whether different framings explaining the rationale for the policy change public support for prison nutrition standards. The study will also explore whether demographic characteristics, such as political affiliation or previous interaction with the criminal legal system moderate the effect of policy rationale on public support. This document pre-specifies our planned analytic approach prior to data collection.

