### **Statistical analysis plan**

#### **Predictions**

We predict that public support will be higher among participants who are assigned any of the 3 policy rationales vs. no rationale (control). We do not have predictions as to which rationale will elicit the highest public support.

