#### **Statistical methods**

Using linear regression, we will regress policy support on indicator variables for the experimental arm, excluding the control arm as referent. In this model, policy support will be treated as a continuous variable with responses ranging from 1 (representing strongly oppose) to 5 (strongly support). Analyses will estimate average differential effects (ADE, differences in predicted means) for each rationale compared to the control. We will use a two-sided critical alpha of 0.05 to conduct all statistical tests. All confidence intervals presented will use a 95% confidence level. We will then use pairwise comparisons to compare the predicted outcomes for each rationale to one another, using Bonferroni-Holm corrected p-values, to adjust for these 3 additional post-hoc tests.

We will use linear regression to examine correlates of policy support. We will regress policy support on the following demographic characteristics in a multivariable model:

- Reason for policy (experimental arm, with control arm as referent)
- Age
- Gender
- Race/ ethnicity
- Income
- Education
- Political party affiliation
- Having prior interactions with the criminal legal system
- Holding biases toward people who are incarcerated

For all analyses, we will exclude participants who complete <90% of the survey or who complete the survey implausibly quickly (defined as <1/3 of the median completion time).

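### The exploratory moderation aim has no matching analysis: the only model containing the characteristics estimates correlates of support, not differences in rationale effect

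*SAP*

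**What the plan says.** The SAP's Introduction gives two aims. The main one is "Specifically, we aim to examine whether different framings explaining the rationale for the policy change public support for prison nutrition standards". The second is exploratory: "The study will also explore whether demographic characteristics, such as political affiliation or previous interaction with the criminal legal system moderate the effect" of rationale on support. The same section closes with "This document pre-specifies our planned analytic approach prior to data collection".

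Statistical methods gives two sets of analyses:

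- **Arm comparisons.** Support, scored 1 to 5, is regressed on arm indicators to estimate each rationale's average differential effect (ADE) against control. Three Holm-corrected comparisons between rationales follow.
- **Correlates.** The purpose is stated as "We will use linear regression to examine correlates of policy support", and the model as "We will regress policy support on the following demographic characteristics in a multivariable model". The list that follows has nine entries: the experimental arm and eight characteristics. Both characteristics named in the Introduction are among them ("Political party affiliation" and prior contact with the criminal legal system), each as an entry of its own.

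No interaction term, subgroup effect or test of heterogeneity appears anywhere in the SAP.

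**The concern.** Moderation means that the effect of a rationale differs between groups, for example that a cost-saving argument moves one party's supporters more than another's. A model with arm and party as separate terms assumes that each rationale has the same effect in every group. Its party coefficient answers another question: whether support is higher in one group than in another, averaged over arms.

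The first aim therefore has its analysis and the second has none. What is at stake is one exploratory question. Followed to the letter, the plan leaves it unanswered. If the question is taken up later, the moderators, their coding, the form of the test and the handling of multiplicity would be chosen without pre-specification, in a document whose purpose is to pre-specify.

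**Working it through.** **Aims against analyses**

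| Introduction | Statistical methods |
|---|---|
| Do rationales change support? | ADEs against control; three comparisons between rationales |
| Do characteristics moderate that effect? (exploratory) | None stated |
| None stated | Correlates of support |

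**What the additive model estimates**

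Assumptions, none of them in the SAP: four equal randomised arms, a binary party variable with prevalence p in group A, and the same effect for all three rationales within a group (eA in group A, eB in group B). Let g0 be the party gap in the control arm. The gap under each rationale is then g0 + (eA − eB). The additive model's expected coefficients are:

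- each arm: p·eA + (1 − p)·eB
- party: the mean gap over four arms, [g0 + 3(g0 + eA − eB)]/4 = g0 + 0.75(eA − eB)

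With p = 0.50, in points on the 1 to 5 scale:

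| Case | eA | eB | g0 | Arm coefficient | Party coefficient |
|---|---|---|---|---|---|
| 1. No moderation | 0.30 | 0.30 | 0.60 | 0.30 | 0.60 + 0 = 0.60 |
| 2. Moderation | 0.60 | 0 | 0.15 | 0.30 | 0.15 + 0.45 = 0.60 |
| 3. Opposite effects | 0.30 | −0.30 | −0.45 | 0 | −0.45 + 0.45 = 0 |

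Cases 1 and 2 cannot be told apart by these coefficients, although only case 2 has moderation. In case 3 every coefficient is zero although the effects differ by 0.60 points.

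The control gaps were chosen to produce the match. With g0 held at 0.60 and the effects of case 2, the party coefficient is 0.60 + 0.75 × 0.60 = 1.05. With effects of 0.60 and 0 at other prevalences, the arm coefficient is 0.30 × 0.60 = 0.18 (p = 0.30) or 0.20 × 0.60 = 0.12 (p = 0.20). The cases show that the coefficients *can* coincide, which is enough to show that they do not identify moderation.

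**What an interaction model adds**

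In a simulation of the three cases (n = 1,200, four equal arms, normal errors with an assumed SD of 1.2, 2,000 runs each), a joint arm-by-moderator test rejected in 4.4%, 88% and 89% of runs. It separates the cases.

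**Precision of that model**

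The sample of about 1,200 was set by the parent study and cannot be reproduced, because no effect size, SD or power is given. Assume 1,200/4 = 300 per arm, SD 1, two-sided alpha 0.05 and 80% power, so the multiplier is 1.960 + 0.842 = 2.802.

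- One rationale against control: 2.802 × √(2/300) = 0.23 SD.
- Difference in that effect between two groups: SE = √[2/(300p) + 2/(300(1 − p))].
  - p = 0.50: SE 0.163, detectable 0.46 SD
  - p = 0.30: SE 0.178, detectable 0.50 SD
  - p = 0.20: SE 0.204, detectable 0.57 SD

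Power for an interaction of 0.23 SD is 29%, 25% and 20% respectively.

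**The case against.** The best defence is that the two sections do not strictly contradict each other. Statistical methods calls its model an analysis of correlates and never claims that it tests moderation. Both sections can be true, with one exploratory aim lacking an analysis and one analysis lacking a listed aim. That is a fair description, and it is the point made here: a gap between aim and analysis. Nor is the absence of moderation from the Predictions section a defect, since an exploratory question needs no prediction.

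It may also be said that a multivariable model could contain interactions. The list shows none and the stated purpose is correlates. If interactions are meant, the text has to say so.

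Three stronger readings are tempting, and the SAP does not support them:

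- *The correlates coefficients will be reported as moderation.* Nothing in the plan says so, and the model's own label points the other way. That harm is hypothetical.
- *The additive coefficients are always the same with and without moderation.* They are not. With the control gap fixed, the party coefficient moves from 0.60 to 1.05 in the example above.
- *The main results are compromised.* The ADEs and the comparisons between rationales come from a separate model and do not depend on this.

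**Conclusion.** The point holds, and it is minor. The SAP states an exploratory moderation aim, says that it pre-specifies the analytic approach, and gives no analysis with a parameter for moderation. Carried out as written, with the correlates model read as additive, the plan cannot answer that aim. This conclusion rests on the text alone; the numerical cases only illustrate it, and their effects, gaps and prevalences are assumed.

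The detectable differences also rest on assumptions that the SAP does not state: equal allocation, no exclusions and a binary moderator. With 10% excluded (270 per arm, assumed) they rise to 0.24 SD for an arm contrast and 0.48 to 0.60 SD for an interaction.

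**What to change.** **Preferred: keep the aim and give it an analysis.** In Statistical methods, add an exploratory linear model with arm-by-moderator interaction terms for the two characteristics named in the Introduction, and state how each is coded. Use one joint interaction test per moderator and report rationale effects by subgroup with 95% confidence intervals. Apply a Holm correction across the moderators tested, or state that the tests are uncorrected and hypothesis-generating. This needs saying because the plan's present correction covers only the three comparisons between rationales. If independent, two uncorrected tests at 0.05 carry a 1 − 0.95² = 9.8% chance of at least one false positive; testing all eight listed characteristics would carry 1 − 0.95⁸ = 34%. State that the correlates coefficients are not to be read as moderation, and list correlates among the aims.

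**Alternative: drop the aim.** Replace the moderation sentence in the Introduction with the correlates aim that is analysed.

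**Cost.** The first option takes a few sentences before data collection, with no extra participants and no extra survey items, since both variables are already in the correlates model. Its drawback is low precision: the plan should say that a null interaction result would not show absence of moderation. The second option takes one sentence and gives up the moderation question.

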### **Study protocol**

In an online survey, participants will be asked to imagine a new U.S. policy which would require prisons to serve meals that meet the government definition of healthy. In a between-subjects experiment, participants will be randomly assigned to view 1 of 3 different rationales for the new policy—public safety, right-to-health, or cost-saving—or be assigned to a control arm where no rationale is given. After viewing the rationale, participants will be asked whether they would strongly support, somewhat support, neither support or oppose, somewhat oppose, or strongly oppose the policy. Participants will also answer demographic questions.

### **Statistical analysis plan**

#### **Predictions**

We predict that public support will be higher among participants who are assigned any of the 3 policy rationales vs. no rationale (control). We do not have predictions as to which rationale will elicit the highest public support.

#### **Statistical methods**

Using linear regression, we will regress policy support on indicator variables for the experimental arm, excluding the control arm as referent. In this model, policy support will be treated as a continuous variable with responses ranging from 1 (representing strongly oppose) to 5 (strongly support). Analyses will estimate average differential effects (ADE, differences in predicted means) for each rationale compared to the control. We will use a two-sided critical alpha of 0.05 to conduct all statistical tests. All confidence intervals presented will use a 95% confidence level. We will then use pairwise comparisons to compare the predicted outcomes for each rationale to one another, using Bonferroni-Holm corrected p-values, to adjust for these 3 additional post-hoc tests.

We will use linear regression to examine correlates of policy support. We will regress policy support on the following demographic characteristics in a multivariable model:

- Reason for policy (experimental arm, with control arm as referent)
- Age
- Gender
- Race/ ethnicity
- Income
- Education
- Political party affiliation
- Having prior interactions with the criminal legal system
- Holding biases toward people who are incarcerated

For all analyses, we will exclude participants who complete <90% of the survey or who complete the survey implausibly quickly (defined as <1/3 of the median completion time).

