### **Sample size needs**

This study will occur as an auxiliary study to an experiment examining the impact of nudges on improving the healthfulness and environmental sustainability of grocery purchases (i.e., the parent study). The total sample size (~1,200 participants) was calculated based on the anticipated effect sizes in the parent study.

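### Optional improvement: the arm-only model for the rationale effects is valid, but pre-specified adjustment for five demographics already planned could add a little precision

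*SAP*

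**What the plan says.** Only the SAP is at hand. Its Study protocol section describes a between-subjects experiment in which "participants will be randomly assigned to view 1 of 3 different rationales for the new policy", with a further arm given no rationale. Under Statistical methods the main model is: "Using linear regression, we will regress policy support on indicator variables for the experimental arm, excluding the control arm as referent". Its target is also stated: "Analyses will estimate average differential effects (ADE, differences in predicted means) for each rationale compared to the control". The three comparisons between rationales then use the predicted outcomes, with Holm-corrected p-values.

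A second model has a different purpose: "We will use linear regression to examine correlates of policy support". It contains arm, age, gender, race/ethnicity, income, education, party affiliation, prior contact with the criminal-legal system, and an attitude item, "Holding biases toward people who are incarcerated". Nothing says that the effects or contrasts are taken from it.

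On data collection the SAP says "Participants will also answer demographic questions", without fixing when each item is asked relative to the rationale. On exclusions: "For all analyses, we will exclude participants who complete <90% of the survey"; implausibly fast completers are also removed. A retained respondent can therefore have blank covariate items.

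**The concern.** The total of about 1,200 was set by the parent study's anticipated effects, not by this outcome (Sample size needs). Precision for policy support therefore has to come from the analysis. In a linear model, adjusting for characteristics that the rationale cannot change leaves the difference in means as the target and removes the outcome variance that those characteristics explain. Five such characteristics are already planned and modelled as correlates of support, but the main estimates do not use them. What is at stake is the width of the intervals and some power, not bias or validity.

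**Working it through.** **The plan's own figure.** The total of about 1,200 cannot be reproduced for this outcome, because the SAP gives no effect size, SD or power for policy support. The check therefore asks what adjustment would gain or cost at that total.

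**Inputs from the SAP:** N about 1,200; four arms; two-sided alpha 0.05; linear model.

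**Assumed, not in the SAP:** equal allocation (1,200/4 = 300 per arm); a true effect of 0.20 SD; R² of the covariates of 0 to 0.10; 14 degrees of freedom for the five demographics plus one missing category each, so k = 14 + 5 = 19.

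**Arm-only model.** SE = √(2/300) = 0.0816 SD. Power at 0.20 SD is 0.687. The difference detectable with 80% power is 0.229 SD.

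**Adjusted model.** Variance factor = (1 − R²)(N − 5)/(N − 5 − k) = (1 − R²) × 1195/1176. The SE ratio to the arm-only model is its square root.

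| R² | Variance factor | SE ratio | CI width | Power at 0.20 SD | Detectable difference (SD) |
|---|---|---|---|---|---|
| 0 | 1.0162 | 1.008 | +0.8% | 0.680 | 0.2308 |
| 0.02 | 0.9958 | 0.998 | −0.2% | 0.689 | 0.2285 |
| 0.05 | 0.9653 | 0.983 | −1.7% | 0.702 | 0.2249 |
| 0.10 | 0.9145 | 0.956 | −4.4% | 0.726 | 0.2189 |

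Break-even R² = 19/1195 = 0.016. Below that, adjustment loses slightly.

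**Skipped items.** If respondents with any blank covariate are dropped, no missing categories are needed and k = 14. The loss that cancels the gain is 1 − (1 − R²) × 1195/1181: 3.9% of respondents at R² 0.05 and 8.9% at R² 0.10. Skipping of 1% on each of five items already keeps only 0.99⁵ = 95.1%, a loss of 4.9%.

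**Simulation.** The set-up was a 1–5 outcome, 300 per arm, 3% random skipping per item and 3,000 runs, with R² on the latent scale. With missing categories, the SE ratio to arm-only was 1.011, 0.988 and 0.954 at R² 0, 0.05 and 0.10. With complete cases it was 1.086, 1.064 and 1.031. At R² 0.10 the mean effect was 0.235 in both the arm-only and the adjusted model, so the target does not move.

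**Why the covariate set must be restricted.** Suppose the bias item is asked after the rationale and the rationale lowers it by 0.2, with a slope of −0.4 on support and a direct effect of 0.15. The total effect is 0.15 + 0.4 × 0.2 = 0.23. In simulation the arm-only model returned 0.23, and the model adjusted for bias returned 0.15.

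**The case against.** The strongest reply is that nothing here is wrong. The arm-only model is unbiased, its target, coding, alpha and correction for the pairwise tests are stated, and it needs no covariate coding, missing-item rule or assumption about question order. That stands, and it is why the point is optional.

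The gain is also small. At R² 0.02 it is negligible, and the SAP gives no R². The missing-category columns and the cost of skipped items reduce it further. This stands too, and the figures above include those columns.

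It may be said that adjusted arm coefficients are already planned, since arm is the first term in the correlates model. That stands only in part. The model is assigned to correlates, and it includes the bias item, whose timing is not stated, so it cannot simply be read as giving adjusted versions of the stated effects.

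Two stronger readings are tempting. A reader might infer that leaving covariates out biases the effects or makes the tests invalid; random assignment rules that out. A reader might also expect much larger gains from party affiliation and prior criminal-legal contact. The SAP gives neither how strongly these predict support nor when they are asked, so it does not support such gains.

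**Conclusion.** This is an optional improvement, not an error. The planned model is valid but forgoes some precision that five demographics already planned might supply. The size is modest: intervals narrower by 0.2% to 4.4% and power at 0.20 SD higher by between 0.002 and 0.04 for R² from 0.02 to 0.10, against a cost of about 1% in the standard error if the covariates explain nothing. These figures rest on equal allocation, the assumed effect, R² and degrees of freedom, and on keeping respondents with skipped items. They also assume that skipping an item does not depend on the rationale shown. Leaving the SAP as it is would not undermine the study.

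**What to change.** State in Statistical methods that the effects against control and the three pairwise contrasts come from a linear model with arm plus age, gender, race/ethnicity, income and education. Fix the coding of each, and keep respondents with a skipped item by means of a missing category. Report the arm-only model as a sensitivity analysis. Leave out the bias measure. Add party affiliation or prior criminal-legal contact only if asked before the rationale or justified as unaffected by it, and say which applies.

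The cost is a few sentences, no new survey items, about 19 degrees of freedom out of about 1,200, and a little more analysis work. The SAP says that it was written before data collection, but does not show whether data have since been collected. If outcomes have been seen, the adjusted model should be labelled as added later.

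### Must the plan fix a decision rule, or a Holm correction, for the three rationale-versus-control tests?

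*SAP*

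**What the plan says.** The SAP's Introduction gives the aim as finding out "whether different framings explaining the rationale for the policy change public support for prison nutrition standards". The Predictions section expects that "public support will be higher among participants who are assigned any of the 3 policy rationales vs. no rationale (control"), and adds: "We do not have predictions as to which rationale will elicit the highest public support".

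The Statistical methods section sets one linear regression on arm indicators with control as the reference. "Analyses will estimate average differential effects (ADE, differences in predicted means) for each rationale compared to the control". On the level it says: "We will use a two-sided critical alpha of 0.05 to conduct all statistical tests". Confidence intervals are at 95%. The three comparisons among rationales come afterwards, "using Bonferroni-Holm corrected p-values, to adjust for these 3 additional post-hoc tests".

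The section contains no omnibus test, no pooled contrast of all rationale arms against control, and no statement of which combination of the three control contrasts confirms the prediction.

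**The concern.** Two things look wrong at first.

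- **The verdict on the prediction is not fixed.** 'Any of the three' could mean each rationale, at least one, or all rationale participants pooled. The Introduction says "This document pre-specifies our planned analytic approach prior to data collection", yet if one or two of the three contrasts were significant and positive, an 'at least one' reader would call the prediction supported and an 'all three' reader would not.
- **The correction seems to sit on the wrong family.** Holm protects the comparisons on which the authors make no prediction. The three tests that bear on the prediction have no protection.

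At stake would be a false-positive rate above the stated level, and a reading of 'any' chosen after the data are seen.

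**Working it through.** The plan states no familywise error rate or power for these contrasts, so there is no figure of its own to reproduce. The check asks what each reading implies.

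**Inputs**
- Two-sided 0.05 per test, so c = 1.960 and 0.025 in the predicted direction (Statistical methods).
- Three contrasts sharing one control arm (Statistical methods).
- About 1,200 participants (Sample size needs).
- Assumed: equal allocation, 300 per arm. The SAP gives no ratio.
- Assumed: a common effect d of 0.20, 0.23 or 0.30 SD. The SAP gives no effect size for this experiment.

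**Correlation between contrasts**

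ρ = n/(n + n₀), where n is the size of each rationale arm and n₀ that of control. Here ρ = 300/600 = 0.5.

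**No true effects**

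At least one significant, either direction:

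1 − ∫ φ(u) [Φ((c − √ρ·u)/√(1−ρ)) − Φ((−c − √ρ·u)/√(1−ρ))]³ du = 0.1254

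Dropping the lower-tail term gives the predicted direction only: 0.0627. If the contrasts were independent, the values would be 1 − 0.95³ = 0.1426 and 1 − 0.975³ = 0.0731. Over ρ from 0.33 to 0.67 (unequal allocation), the either-direction figure runs from 13.5% to 11.2% and the positive figure from 6.8% to 5.6%.

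| Reading of the prediction | False confirmation, predicted direction | Nominal |
|---|---|---|
| Each rationale judged separately | 2.5% per test | 2.5% |
| All three required | 0.16% with no effects; at most 2.5% | 2.5% |
| Pooled contrast | 2.5% | 2.5% |
| At least one, uncorrected | 6.3% | 2.5% |
| At least one, Holm (first step 0.05/3) | 2.2% | 2.5% |

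The 2.5% ceiling for 'all three' holds because the joint claim is false only if some rationale has no positive effect, and that rationale's own test must still come out significant and positive. Because the prediction is directional, the error rate to compare is 6.3% with 2.5%. The 12.5% includes significant results in the wrong direction, which could not confirm it.

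**With effects, 300 per arm**

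For d = 0.20, the mean of each test statistic is 0.20/√(2/300) = 2.449, so power for one rationale is Φ(2.449 − 1.960) = 0.688. The joint figures come from the same integral with shifted means, and the Holm figures from simulation.

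| d (SD) | One rationale, uncorrected | One rationale, Holm | All three | At least one, uncorrected | One or two but not three |
|---|---|---|---|---|---|
| 0.20 | 0.69 | 0.60 | 0.45 | 0.892 | 0.892 − 0.454 = 0.44 |
| 0.23 | 0.80 | 0.74 | 0.62 | 0.952 | 0.952 − 0.618 = 0.33 |
| 0.30 | 0.96 | 0.94 | 0.90 | 0.996 | 0.996 − 0.896 = 0.10 |

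Split results would therefore be common at small effects. They affect a verdict only if the choice lies between 'all three' and uncorrected 'at least one'.

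**Which reading the text supports**

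In the Predictions section, 'any' qualifies the participants who are compared with control, and each of them sees a single rationale. The phrase most naturally means whichever rationale they were given. The Statistical methods section matches this, with one difference per rationale and no pooled contrast. Neither section says that one success out of three would be enough.

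**Would Holm on the control contrasts help regardless of the reading?**

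It is needed only under 'at least one'. Under 'all three' it can clash with the joint claim. Three positive differences, each with p = 0.03, satisfy that rule at 0.05, yet every Holm p-value is 3 × 0.03 = 0.09. By simulation, at least one contrast fails Holm although all three are significant at 0.05 in about 2% of trials at d = 0.20.

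**The case for a change.** The strongest case for a change is that linking a prediction to its tests is the job of an SAP, and that this one contains both without the link. The convention of leaving planned contrasts uncorrected does not say which pattern of results confirms a prediction. Split patterns cannot be dismissed either, since "The total sample size (~1,200 participants) was calculated based on the anticipated effect sizes in the parent study" and no effect size is given here. If only one rationale worked, at 0.30 SD, one or two but not all three contrasts would be significant and positive about 95% of the time. A sentence would cost almost nothing.

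Part of this stands. The link is not written down, the arithmetic is right, and a sentence stating what 'any' means would do no harm. But in the case where one rationale works, the plan already requires three separate differences with 95% intervals, so the reader sees which rationale worked and which did not. The aim is to learn whether framings change support, and it does not call for a single yes-or-no verdict. The argument that Holm was put on the wrong family does not stand. The section separates planned contrasts with control from additional post-hoc comparisons and corrects the latter, which is a recognisable and defensible choice.

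**Conclusion.** No change to the plan follows. The model, the contrasts, the level and the intervals are all stated, and each remains valid as written. What is missing is a sentence saying how 'any' is to be read. The text favours 'each rationale', and under that reading nothing is inflated, whether the three differences are reported separately or combined in an all-three claim.

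The excess error of about 6.3% against 2.5% arises only if a single significant positive difference is presented as confirming the prediction. That figure assumes equal allocation, and other ratios move it by less than one percentage point.

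Extending Holm to the control contrasts is a trade-off on which statisticians reasonably differ. At 300 per arm it would lower power per rationale from 0.69 to 0.60 at 0.20 SD and from 0.96 to 0.94 at 0.30 SD. Those effect sizes are assumptions, and the sample size is set by the parent study.

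### Optional improvement, not an error: for the three pairwise rationale comparisons, Holm's second step is stricter than 5% familywise control needs, and Shaffer's version would recover about 0 to 9 points of power to show that one rationale beats both others

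*SAP*

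**What the plan says.** Participants are "randomly assigned to view 1 of 3 different rationales for the new policy", or to a control arm that sees none (SAP, Study protocol). The main analysis compares each rationale with control. The plan then adds "pairwise comparisons to compare the predicted outcomes for each rationale to one another", "using Bonferroni-Holm corrected p-values, to adjust for these 3 additional post-hoc tests" (SAP, Statistical methods).

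On the significance level, the same section states: "We will use a two-sided critical alpha of 0.05 to conduct all statistical tests". On the ordering of the rationales, the Predictions section states: "We do not have predictions as to which rationale will elicit the highest public support". On size, the Sample size needs section states: "The total sample size (~1,200 participants) was calculated based on the anticipated effect sizes in the parent study".

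The SAP gives no SD, expected difference, allocation ratio or power for the comparisons between rationales.

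**The concern.** Holm's procedure makes no use of logical links between hypotheses. All pairwise equalities among three means are linked, so Holm guards against a combination that cannot occur: one equality false and both others true. The price falls on the second-smallest p-value.

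That p-value decides whether one rationale can be shown to beat both others, because such a claim needs two of the three tests to be significant. These tests are the plan's only specified comparison of one rationale with another, and the sample size was set for a different study. Power that can be had without more participants and within the same 5% limit is worth considering.

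**Working it through.** **Inputs from the SAP.** Two-sided alpha 0.05; three pairwise tests among three rationales; four arms; about 1,200 participants.

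**Assumptions, because the SAP is silent.** Equal allocation, 1,200 / 4 = 300 per arm; differences of 0.10 to 0.50 SD. The total of about 1,200 rests on the parent study and cannot be reproduced from this document.

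**Step 1: the logic.** Call the rationales A, B and C. If any two of A=B, A=C and B=C hold, so does the third. The number of true nulls is therefore 3, 1 or 0, never 2. With ordered p1 ≤ p2 ≤ p3 the step levels are:

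- Holm: 0.05/3 = 0.0167, 0.05/2 = 0.025, 0.05.
- Shaffer: 0.05/3 = 0.0167, 0.05, 0.05.

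Familywise error under Shaffer is bounded in each case:

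- Three true nulls: an error requires p1 ≤ 0.05/3, with probability at most 3 × 0.05/3 = 0.05.
- One true null: an error requires that single p-value to be ≤ 0.05, with probability at most 0.05.
- No true null: no false rejection is possible.

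Shaffer's levels are never below Holm's, so every Holm rejection is kept.

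**Step 2: where the two differ.** They differ only when p1 ≤ 0.0167 and p2 lies between 0.025 and 0.05. Example: p1 = 0.012 and p2 = 0.030. With equal standard errors and a common leader, these are z = 2.51 and 2.17, so the third contrast has z of about 0.34 and p3 of about 0.73.

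- Holm-adjusted: 3 × 0.012 = 0.036; max(0.036, 2 × 0.030) = 0.060; 0.73.
- Shaffer-adjusted: 0.036; max(0.036, 0.030) = 0.036; 0.73.

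The leader beats both others under Shaffer and only one under Holm.

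**Step 3: a single pair.** At 0.20 SD the standard error is √(2/300) = 0.0816 SD, so the expected z is 0.20 / 0.0816 = 2.45. Power is Φ(2.45 − 2.24) = 58.2% at 0.025 and Φ(2.45 − 1.96) = 68.8% at 0.05.

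**Step 4: power to show that the best rationale beats both others.** Simulation, 400,000 studies per scenario, normal means, SD 1, 300 per arm, one rationale ahead by d and the other two equal. Gains were taken before rounding.

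| d (SD) | Holm | Shaffer | Gain (points) |
|---|---|---|---|
| 0.10 | 5.8% | 8.8% | 2.9 |
| 0.15 | 18.8% | 25.5% | 6.7 |
| 0.20 | 41.8% | 51.1% | 9.3 |
| 0.25 | 67.9% | 76.0% | 8.0 |
| 0.30 | 87.1% | 91.5% | 4.4 |
| 0.40 | 99.3% | 99.7% | 0.3 |

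For evenly spaced means the gain is 5.7 points (0/0.1/0.2), 7.5 (0/0.15/0.3), 3.4 (0/0.2/0.4) and 0.5 (0/0.25/0.5). With 270 per arm, to allow for exclusions, it is 8.9 at 0.20 SD and 8.6 at 0.25 SD. Estimating the variance from all four arms (1,200 − 4 = 1,196 df) barely changes the picture: 41.6% against 50.8% at 0.20 SD.

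Power to find at least one difference is 69.1% under both methods at 0.20 SD, because the first step is identical.

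**Step 5: familywise error, same setting with estimated variance.**

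| Two rationales equal, third higher by | Holm | Shaffer |
|---|---|---|
| 0 (all equal) | 4.4% | 4.4% |
| 0.20 SD | 2.8% | 4.7% |
| 0.25 SD | 3.5% | 4.9% |
| 0.30 SD | 4.2% | 5.0% |
| 2 SD | 5.0% | 5.0% |

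**The case against.** The case for leaving the text alone is a fair one. The SAP names a recognised method, states the family of three tests and the alpha, and the method controls familywise error. The tests are labelled post-hoc, and the only prediction concerns rationale against control. Saying that no ranking is predicted sets no rule that a winner must beat both others. Nor is Shaffer the only alternative: a global test at 0.05 followed by unadjusted pairs is also valid for exactly three groups and gains more over Holm (11.7 points at 0.20 SD, 9.6 at 0.25).

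All of that stands, and it sets the weight of the point. It does not remove the point, since a method that keeps every Holm rejection within the same 5% is available at almost no cost.

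Three stronger readings are tempting, and none is supported:

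- A reader might infer that the planned adjustment is wrong. It is valid, only conservative at one step.
- A reader might infer a fixed loss of 8 to 9 points. That holds near 0.20 to 0.25 SD with one rationale ahead of two equal ones, close to the largest loss in the scenarios tried. The SAP gives no effect size or SD that would select this case.
- A reader might infer that Holm's stricter step has no effect on error at all. It does lower the actual rate, for example to 2.8% against 4.7% at 0.20 SD. What can be said is that the extra strictness is not needed to stay within 5%.

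**Conclusion.** The point holds as an optional gain in efficiency. The validity of Holm's second step at 0.05 follows from the three-mean structure alone and needs no assumption about effect size. The size of the gain does: about 0 to 9 points in power to show that one rationale beats both others, assuming about 300 per arm, equal allocation and normal theory. It is largest for moderate differences and nearly vanishes when differences are large.

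The comparisons with control and the chance of finding at least one difference between rationales are unaffected. Actual familywise error moves closer to 5% without exceeding it. Since naming a best rationale is not a stated objective, the plan remains sound if the authors keep Holm.

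**What to change.** In the SAP, Statistical methods, replace the Holm adjustment for the pairwise comparisons with *Shaffer-corrected (logically constrained Holm) p-values*, and add the rule: for ordered p1 ≤ p2 ≤ p3, the adjusted values are 3 × p1, max(3 × p1, p2) and max(3 × p1, p2, p3), each capped at 1 and compared with 0.05. The rule takes any valid p-values, including those from robust standard errors.

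The cost is one sentence and one line of code, with no extra participants. The price in error is the rise in actual familywise error shown above, inside the 5% that the plan already accepts. The change should be made before data collection, the stage at which the SAP's Introduction places this document. If data have already been seen, Holm should stay as the primary adjustment.
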